Sponsor	NHS R&D National Coordinating Centre for Health Technology Wessex Institute for Health Research & development [name]
	[contact] [contact]
Date	26/11/2007 Version 6

Information contained in this document is the property of Leicester University and is therefore provided to you in confidence for review by you, your staff, or an applicable ethics committee. This information may not be disclosed to others without written approval from the Principal Investigator, except to the extent necessary to obtain informed consent from those persons entering the study. This document may not be reproduced, stored in a retrieval system or transmitted in any form or by any means without prior authorisation from the Principal Investigator. This document must be returned to the Principal Investigator upon request.

	PROTOCOL SYNOPSIS
Title	Randomised controlled trial to evaluate impact of diagnostic testing for influenza, respiratory syncytial virus and Streptococcus pneumoniae infection on the management of acute admissions in the elderly and high risk 18-64-year-olds.
Sponsor	NHS R&D National Coordinating Centre for Health Technology Assessment
Study population	Male or female elderly ( $\geq$ 65 years old) patients, Male or female patients aged $\geq$ 18 years with underlying heart or lung disease including asthma , or pneumonia / influenza type symptoms.
Study setting	Medical Admissions Units in the University Hospitals of Leicester NHS Trust (Leicester Royal Infirmary, Glenfield Hospital, Leicester General Hospital).
Duration	August 1 2005- July 31 2008 (36m). Patient enrolment will occur during September 1 2005 to June 30 2006; September 1 2006 to June 30 2007; & September 1 2007 to June 30 2008 All patients will be followed-up for 28 days.
Rationale	The purpose of this study is to determine the diagnostic accuracy and clinical- and cost-effectiveness of rapid molecular and near patient diagnostic tests for influenza, RSV and S. pneumoniae infections in the elderly, and subjects aged $\geq 18$ years with chronic cardiopulmonary conditions, or pneumonia / influenza type symptoms. in comparison to traditional laboratory culture.
Objectives and hypotheses         1.           2.         3.           4.         5.           6.         7.	for influenza, RSV and S. pneumoniae infections have any impact on the prescription of antimicrobials. To determine whether rapid molecular and near patient diagnostic tests for influenza, RSV and S. pneumoniae infections allow more appropriate use of isolation facilities, in comparison to traditional laboratory culture. To compare the costs of performing rapid molecular and near patient diagnostic tests for influenza, RSV and S. pneumoniae infections, in comparison to traditional laboratory culture. To assess cost-savings associated with earlier use of narrow-spectrum antimicrobial therapy (or avoidance or discontinuation of antibiotics) in patients whose influenza, RSV and S. pneumoniae infections are diagnosed more rapidly by rapid molecular and near patient diagnostic tests, in comparison to traditional laboratory culture.

- 8. To assess the impact that rapid molecular and near patient diagnostic tests have on the costs associated with an inpatient stay and on costs post-discharge up to a maximum of 28 days after admission.
- 9. To assess the impact that rapid molecular and near patient diagnostic tests have on quality-of-life, as measured by the EuroQol, and to use this information to estimate the quality adjusted life years (QALYs) generated during the 28 days after admission.
- 10. To assess the cost-effectiveness of rapid molecular and near patient diagnostic tests in comparison to traditional laboratory culture. This will be done on the basis of both cost per case detected and cost per QALY.
- 11. To explore whether patients with pneumococcal infection have lower levels of cellular and humoral immunity to the pnuemococcus in comparison to patients who do not have pneumococcal infection.

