- 10. Rapid molecular and near patient diagnostic tests are more cost-effective than traditional laboratory culture.
- 11. Patients with pneumococcal infections have lower levels of cellular and humoral immunity to the pneumococcus in comparison to patients who do not have pneumococcal infection

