	
 
Have an acute exacerbation of chronic cardio-pulmonary illness of ≤168 hours (7 days) duration, OR an acute cardio-pulmonary illness or influenza-like illness of ≤7 days duration, including:         
 
Pneumonia,
 
Influenza/influenza-like illness,
 
Exacerbations of chronic obstructive pulmonary disease (COPD),
 
Bronchitis,
 
Asthma,
 
Congestive heart failure,
 
Cardiac arrhythmia;
 
 
 
Able and willing to adhere to the procedures stated in the protocol
 
Patients should have access to a telephone
 

Exclusion criteria	
 
Inclusion criteria not met
 
Angina/suspected myocardial infarction;
 
Were recruited to this study within 28 days of the current admission
 
Could not be recruited into the study within a 16-hour period of initial assessment by a doctor on the Medical Admissions Unit or a ward accepting acute medical admissions;
 
Enrollment in a study of antimicrobial therapy for the illness for which the patient was admitted
 

Randomisation:	Patients in each centre will be randomly allocated to one of three diagnostic policy groups: Group 1: Near patient tests (Quidel – influenza; Binax NOW – pneumococcus); Group 2: rapid molecular tests ('flu & RSV plus laboratory testing of concentrated urine in the Binax NOW assay); and Group 3: traditional laboratory culture, using computer generated randomisation codes stratified by centre.
Assessment methods:	
 
Clinical
 
Impact of test result on prescribing, specifically:- 
 
(a) Earlier use of 'narrow-spectrum' anti-microbial therapy,
 
(b) Earlier switch from intravenous to oral therapy,
 
(c) Avoidance or earlier discontinuation of antibiotics in patients infected with influenza and RSV, and
 
(d) Prescriptions of influenza neuraminidase inhibitors
 
Will be assessed in rapid near patient (Group 1) and molecular diagnostic groups (Group 2) and compared to traditional laboratory culture (Group 3).
 
 
 
2. Clinical outcomes, specifically:- 
 
(a) Length of hospital stay;
 
(b) Fever duration,
 
(c) Supplemental oxygen dependence and CPAP dependence,
 
(d) Deaths
 
Will be assessed in rapid near patient (Group 1) and molecular diagnostic groups (Group 2) in comparison to traditional laboratory culture (Group 3).
 
 
 

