#### Financial

- 6. Costs of diagnostic tests, estimated by means of an 'ingredients' approach where all items needed to carry out the test are recorded and costed using appropriate local and national data, e.g., items to collect and transport specimens, media and reagents for the test, equipment to process specimens, technical support costs, etc. Costs will be identified for the following technologies:
  - (a) Rapid near patient test for influenza (Quidel),
  - (b) Rapid near patient test for pneumococcus (Binax NOW),
  - (c) Molecular (multiplex PCR) tests for influenza A and B and RSV A and B,
  - (d) 'Prompt' antigen detection test for pneumococcus (Binax NOW), using x25 concentrated urine in the laboratory,
  - (e) Culture (blood and sputum) for S. pneumoniae,
  - (f) Gram staining of sputum samples,
  - (g) Cell culture for influenza A and B,
  - (h) Cell culture for RSV A and B,
  - (i) Other tests that may be applied, eg immunofluorescence
- 7. Care costs Cost of inpatient stay will be determined using information on length of stay and hospital costs to determine a 'hotel' cost of routine care. To this will be added the cost of any additional clinical care received such as diagnostic tests, drugs, etc. For patients who are discharged within 28 days of admission, health care resource use in the period after discharge will be recorded using a simple questionnaire administered in a telephone interview. These will be costed using appropriate national data, for example NHS

reference costs unit costs compiled by the PSSRU at the University of Kent.

- 8. Cost-savings, which accrue from (i) a reduction in the use of resources; and (ii) earlier discharge from the hospital, will be identified by comparison of the costs for participants in Groups 1, and 2, compared to traditional laboratory culture (Group 3).
- 9 Economic evaluation of near patient and rapid molecular diagnostic tests will be assessed by two main outcomes measures
  - (a) cost per case detected,
  - (b) cost per QALY

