10. To assess the cost-effectiveness of rapid molecular and near patient diagnostic tests in comparison to the cost/QALY of cases diagnosed correctly by traditional laboratory culture. To assess the costeffectiveness of rapid molecular and near patient diagnostic tests in comparison to traditional laboratory culture. This will be done on the basis of both cost per case detected and cost per QALY.

Rapid molecular and near patient diagnostic tests are more cost-effective than traditional laboratory culture.

11. To explore whether patients with pneumococcal infection have lower levels of cellular and humoral immunity to the pneumococcus in comparison to patients who do not have pneumococcal infection.

Patients with pneumococcal infection have lower levels of cellular and humoral immunity to the Pneumococcus in comparison to patients who do not have pneumococcal infection.

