#### 6.1.13 Randomisation and Trial Identification Numbers

Patients in each centre will be randomly allocated, using computer generated randomisation codes stratified by centre, to one of three diagnostic study groups:

Group 1: Rapid near patient diagnostic tests (influenza and pneumococcus),

Group 2: Rapid molecular tests (influenza & RSV), plus laboratory pneumococcal antigen testing, and Group 3: Traditional 'laboratory culture' (influenza, RSV, and *S. pneumoniae*)]

The randomisation code (i.e., whether in Group 1, 2, or 3) will be included in sequentially numbered study packs that will be stored at each hospital (Leicester Royal Infirmary, Glenfield Hospital, and Leicester General Hospital). The Packs will be labelled as follows:

1-0001, etc, (Leicester Royal Infirmary site One)

**2**-0001, etc, (Glenfield Hospital siteTwo)

**3**-0001, etc, (Leicester General Hospital site Three) which correspond to the Trial Identification Numbers allocated to participants at each study site.

The randomisation codes will be generated by the Department of Health Sciences, University of Leicester. The randomisation code will not be known by the Study Nurse until after the patient has signed the Patient Informed Consent Form. Only then will the study pack containing details of randomisation be opened.

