  First, the proportion of patients with *S. pneumoniae* infection in Groups 1, 2, and 3.
  Second, to better define the burden of influenza and RSV, the proportion of all patients with (i) influenza, and (ii) RSV, who die.
- 3. Quality of life, as measured by EuroQol, and quality adjusted life years generated during the 28 days after admission, will be assessed:
  - (a) In all patients in Groups 1, and 2 in comparison to Group 3.

- (b) Second, in patients in patients with (i) influenza, (ii) RSV, and (iii) *S. pneumoniae* in Groups 1, and 2, in comparison to Group 3.
- 4. Use of isolation facilities
  - (a) The time from admission to the MAU to the time of admission to a single room (isolation cubicle) will be compared for patients with confirmed influenza or RSV in Groups 1, 2, and 3.
  - (b) The proportion of patients with influenza or RSV in Groups 1, 2, and 3 who are isolated at any stage during the first 120 hours of the admission.
  - (c) The proportion of patients with *S. pneumoniae* infection in Groups 1, 2, and 3 who are inappropriately isolated for >12 hours.

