#### 7.5.2 Financial endpoints

- 1. Costs of diagnostic tests, Costs will be identified for:
  - (a) Rapid near patient test for influenza (Quidel);
  - (b) Rapid near patient test for pneumococcus (Binax NOW),
  - (c) Molecular (multiplex PCR) tests for influenza A and B and RSV A and B
  - (d) 'Prompt' antigen detection test for pneumococcus (Binax NOW), using x25 concentrated urine in the laboratory
  - (e) Culture (blood and sputum) for S. pneumoniae
  - (f) Gram staining of sputum samples
  - (g) Cell culture for influenza A and B
  - (h) Cell culture for RSV A and B
  - (i) Other tests that may be applied, eg immunofluorescence
- 2. Care costs Cost of inpatient stay ( $\pm$  95%CI) will be determined for:
  - (a) All patients in Groups 1, 2, and 3;
  - (b) All patients (in all groups) with (i) influenza, (ii) RSV, and (iii) S. pneumoniae infection, and
  - (c) Patients with (i) influenza, (ii) RSV, and (iii) S. pneumoniae infection in Groups 1, 2, and 3.

For patients who are discharged within 28 days of admission, health care resource use in the period after discharge will be recorded using a simple questionnaire administered in a telephone interview.

- 3. Cost-savings that accrue from earlier use of narrow-spectrum antibiotics, oral therapy, or avoidance, or discontinuation of antibiotics will be assessed in
  - (a) All patients in Groups 1, 2, and 3;
  - (b) Patients with (i) influenza, (ii) RSV, and (iii) S. pneumoniae infection in Groups 1, 2, and 3,
- 4. Economic evaluation of near patient and rapid molecular diagnostic tests will be assessed by two main outcomes measures
  - (a) Cost per case detected,
  - (b) Cost per QALY

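### Objective 10, hypothesis 10 and the QALY endpoint name only culture as comparator, so the protocol states no cost-effectiveness comparison between the two rapid policies it randomises

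*Protocol*

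**What the plan says.** **Three policies are randomised.** Patients "will be randomly allocated to one of three diagnostic policy groups" (Synopsis, Randomisation): near patient tests (Group 1), molecular tests with laboratory pneumococcal antigen (Group 2) and culture (Group 3). Section 6.1.13 repeats this.

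**Where a cost-effectiveness comparator is named, it is culture.**
- Synopsis, Objectives, item 10: "To assess the cost-effectiveness of rapid molecular and near patient diagnostic tests in comparison to traditional laboratory culture", on both cost per case detected and cost per QALY.
- Section 2.1, objective 10, repeats that sentence and puts another before it, which sets the rapid tests in "comparison to the cost/QALY of cases diagnosed correctly by traditional laboratory culture".
- Synopsis, Hypotheses, item 10: "Rapid molecular and near patient diagnostic tests are more cost-effective than traditional laboratory culture".
- Section 7.5.1, item 3(a), and the matching Synopsis endpoint, for quality of life and QALYs: "In all patients in Groups 1, and 2 in comparison to Group 3".

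**Elsewhere the three groups are treated together, or no comparator is named.**
- Section 7.5.2, item 4: economic evaluation "of near patient and rapid molecular diagnostic tests will be assessed by two main outcomes measures", cost per case detected and cost per QALY, with no comparator.
- Section 7.5.2, items 2 and 3: care costs and cost-savings are assessed in all three groups.
- Section 7.6: EQ-5D is compared across the three groups, and the cost analysis aims at an unbiased view of cost differences among them.
- Section 7.3, closing paragraph: one basis for evaluation is the three strategies set against one another.

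**The concern.** The three policies are mutually exclusive: a hospital would adopt one of them. When three such options compete, the useful question about a dearer option is what its extra cost buys over the next cheaper one. A ratio against a common baseline answers a different question, namely whether the option beats doing what is done now. Two options can both pass that test while one is poor value beside the other.

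An analyst who implements objective 10, hypothesis 10 and the QALY endpoint as worded would report two ratios, each against Group 3. Hypothesis 10 could then be supported for both rapid policies and still leave open which one to choose, although the randomised data to answer that would be in hand.

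**Working it through.** The protocol states no cost, QALY, ratio or threshold, so there is no figure to reproduce. The check has two parts: what the text specifies, and whether two ratios against culture are enough to rank the policies.

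**1. Does any section supply the missing contrast?**
- Section 7.6, Cost Data: costs across three groups, but no effect measure.
- Section 7.6, EQ-5D: scores across three groups, but QALYs are not mentioned and nothing is combined with cost.
- Section 7.3: says which populations and strategies are evaluated, but sets no cost-effectiveness contrast.
- Section 7.5.2, item 4: the two economic measures, with no comparator, so objective 10 is the only text that supplies one.
- The second sentence in Section 2.1, objective 10: a ratio within culture-diagnosed cases, not an increment between randomised policies.

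So a cost-effectiveness comparison of Group 2 with Group 1 is neither stated nor ruled out.

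**2. Can ratios against culture rank the policies?** All inputs below are assumed. Increments are against culture, costs in pounds.

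Formulas: ratio = extra cost / extra QALY; net benefit = threshold × extra QALY − extra cost.

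Near patient in every case: +5 and +0.0010 QALY. Ratio 5 / 0.0010 = 5,000. Net benefit is 20 − 5 = 15 at 20,000 per QALY and 30 − 5 = 25 at 30,000.

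| Case | Molecular v culture | Ratio v culture | Molecular v near patient | Molecular net benefit at 20,000 | at 30,000 |
|---|---|---|---|---|---|
| A | +30, +0.0016 | 18,750 | 25 / 0.0006 = 41,667 | 32 − 30 = 2 | 48 − 30 = 18 |
| B | +56.25, +0.0030 | 18,750 | 51.25 / 0.0020 = 25,625 | 60 − 56.25 = 3.75 | 90 − 56.25 = 33.75 |
| C | +15, +0.0018 | 8,333 | 10 / 0.0008 = 12,500 | 36 − 15 = 21 | 54 − 15 = 39 |

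In all three cases both rapid policies pass against culture at either threshold. In A, near patient is the better value at both thresholds (15 against 2; 25 against 18). In C, molecular is (21 against 15; 39 against 25). A and B have the same pair of ratios against culture, 5,000 and 18,750, yet at 30,000 near patient is better in A (25 against 18) and molecular in B (33.75 against 25). The two ratios therefore do not determine the choice; the increments behind them are needed.

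**3. Uncertainty and precision.** Point estimates for Group 2 against Group 1 follow by subtracting the increments against culture. Their uncertainty does not follow from two separate intervals, because both share Group 3. With n per group and a common SD σ (an assumption), the standard error of Group 2 minus Group 1 is σ√(2/n). Treating the two differences from culture as independent would give σ√(4/n), too large by √2 = 1.41. Precision is no obstacle: with the protocol's 2752 elderly patients and 20% dropout, 2752 × 0.8 / 3 = 734 per group, the same for every pair.

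**The case against.** The strongest reply is that the framing loses nothing. Costs and EuroQol are collected in every arm, Section 7.6 analyses both across three groups, and Section 7.3 sets the strategies against one another. Anyone given the incremental costs and effects against Group 3 can subtract. Testing new policies against current practice is a legitimate objective, and the mechanics of an incremental analysis usually sit in an analysis plan, which is not shown here.

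Much of this stands. It does not remove the point, because the comparator is not left to a later plan: the objective, hypothesis and QALY endpoint state it. A plan faithful to them need report only two ratios, which the working shows are not enough to rank the policies.

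Some stronger readings do not hold:
- *The protocol never compares the rapid policies, or the design prevents it.* Sections 7.3 and 7.6 contradict this, and Section 7.5.2, item 4, does not restrict the comparator.
- *The cost-savings item fixes culture for the economic measures.* That Synopsis item says savings "will be identified by comparison of the costs for participants in Groups 1, and 2, compared to traditional laboratory culture (Group 3"), but it concerns savings only. Cost per case and cost per QALY are a separate item, and Section 7.5.2 assesses savings in all three groups.
- *The plan would lead to adopting the wrong policy.* The protocol contains no rule that adopts a policy because it passes against culture.
- *Cost per case is invalid because Group 1 has no rapid RSV test.* Section 6.2.1 shows that Group 1 still receives RSV culture results. Extra RSV detection in Group 2 is a real effect of that policy, so separate RSV reporting is a preference.

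**Conclusion.** The point holds as a worthwhile improvement. The cost-effectiveness objective, hypothesis 10 and the QALY endpoint name only culture. No cost-effectiveness comparison of Group 2 with Group 1 is stated, and the sections that treat the three groups together do not supply one. Ratios against culture alone can make both rapid policies look acceptable and leave the choice between them open.

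Its size in this trial cannot be given. The worked cases rest entirely on assumed costs, QALYs and thresholds, and they favour either rapid policy depending on the inputs. They show that the stated comparison is insufficient; they do not predict which policy is better value. The conclusion also assumes that the three policies are real alternatives for adoption, which the randomisation implies.

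**What to change.** Reword objective 10 in the Synopsis and Section 2.1, hypothesis 10, and the QALY endpoint in the Synopsis and Section 7.5.1, so that all three policies are compared with one another. Suggested objective: *to compare the cost-effectiveness of the three randomised policies by a full incremental analysis of cost per QALY and cost per case detected.* In Section 2.1, drop the sentence about culture-diagnosed cases or reconcile it with this.

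State the analysis in brief:
1. Rank the policies by mean cost.
2. Remove any policy that is dominated or extendedly dominated.
3. Give each remaining ratio against the next less costly policy.
4. Show net benefit with its uncertainty for all three together, over a stated range of thresholds, from a joint analysis that respects the shared groups.

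The comparison with culture can stay as part of this. Reporting cost per case for RSV separately is optional.

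Cost: wording and a little more analysis. No new data, patients or follow-up are needed.

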#### **Hypotheses:**

- 1. The increased diagnostic accuracy of rapid molecular and near patient tests over traditional laboratory methods improves patient management through better use of antimicrobials and isolation facilities. Rapid molecular and near patient diagnostic tests for influenza, RSV and *S. pneumoniae* infections are more cost-effective than traditional laboratory diagnostic tests.
- Rapid molecular and near patient diagnostic tests for influenza, RSV and *S. pneumoniae* infections provide benefits in terms of (a) ease of use, and (b) more rapid results, in comparison to traditional laboratory culture.
- 3. Rapid molecular and near patient diagnostic tests for influenza, RSV and *S. pneumoniae* infections result in earlier use of 'narrow-spectrum' antimicrobial therapy; an earlier switch from intravenous to oral therapy; and earlier discontinuation of antibiotics in patients infected with influenza and RSV in comparison to traditional laboratory culture
- 4. Rapid detection of influenza and RSV by rapid molecular and near patient diagnostic tests leads to the appropriate isolation of patients, but only in hospitals/wards having an adequate provision of cubicles.
- 5. The costs of performing rapid molecular and near patient diagnostic tests for influenza, RSV and *S. pneumoniae* infections, differ significantly from the cost of traditional laboratory culture.
- 6. The earlier use of narrow-spectrum antimicrobial therapy (or avoidance or discontinuation of antibiotics) in patients whose influenza, RSV and *S. pneumoniae* infections are diagnosed more rapidly by rapid molecular and near patient diagnostic tests results in significant cost-savings, in comparison to traditional laboratory culture.
- 7. A streamlining of antimicrobial prescribing that may arise from more rapid diagnosis of influenza, RSV and *S. pneumoniae* infections by rapid molecular and near patient diagnostic tests does not adversely affect patient outcome.
- 8. Any increase in costs incurred by rapid molecular and near patient diagnostic tests, in comparison to traditional laboratory culture, are more than offset by savings that arise from either rational antimicrobial prescribing or earlier discharge from the hospital.
- 9. Rapid molecular and near patient diagnostic tests result in an improvement in quality-of-life, as measured by the EuroQol, which arises from streamlining of antibiotics and earlier discharge into the community.
- 10. Rapid molecular and near patient diagnostic tests are more cost-effective than traditional laboratory culture.
- 11. Patients with pneumococcal infections have lower levels of cellular and humoral immunity to the pneumococcus in comparison to patients who do not have pneumococcal infection

